3.6.5.2 Clinical interview

A clinical interview is conducted after the subject has enrolled in the study but prior to the beginning of the intervention. The aim of the clinical interview is to evaluate the subject inclusion and exclusion criteria.

The subject's MDD diagnosis is evaluated using the MINI International Neuropsychiatric Interview Module A, Major Depressive Disorder (Sheehan et al., 1998). We use MINI version 6.0 that has been translated into Finnish. Only the patients who fulfil the criteria for MDD are included in the study.

We are aware that the inclusion criteria for study is MDD of which the symptoms by definition include suicidal thoughts. At the same time, the threat of self-harm is an exclusion criteria for the study. Should the patient indicate suicidal thoughts or deeds in the interview, they are pursued further in order to evaluate whether the subject meets the exclusion criteria for threat of self-harm.

If the subject has suicidal thoughts but the subject is aware of the thoughts and it is clear that they are not intending to act on them, the subject may be included in the study. If the suicidal thoughts are excessive, the subject is considerably hopeless, has explicit plans or intention of suicide, they are excluded from the study.

If the CSC is not certain whether to include the subject into the study or not, MINI Module B, Suicidality, is conducted. A score of 17 or more points is used as a definitive cut-off point, yet the CSC may use a lower score at their discretion.

The exclusion criteria “They have addiction to digital games” includes addiction to both entertainment games and gambling, and CSC asks the subject of both. If CSC is uncertain whether the subject suffers from gambling addiction, they conduct the Problem Gambling Severity Index (PGSI) as an interview holding 8 points as absolute exclusion criteria, however, they can use a lower cutoff point based on their evaluation. If CSC is uncertain about a subject's addiction to digital games, they conduct Game Addiction Scale (GAS) as an interview, holding four or more answers of “sometimes” or more frequently as absolute exclusion criteria, however, the CSC may hold a lower threshold if necessary.

When needed, the subjects are guided towards their healthcare providers and other health resources as needed.

Also other inclusion and exclusion criteria are evaluated in an interview with the subject. If the subject does not meet the inclusion criteria or that they do meet the exclusion criteria, the subject is not admitted further to the study.

The clinical interview is conducted by clinical subject coordinators (CSCs) who are licensed healthcare professionals. The CSCs are trained to use MINI and have an in-depth understanding of the clinical investigation plan. The clinical interview is described in Appendix 5 - Clinical subject coordinator phone call.

3.6.6 Monitoring plan

3.6.6.1 The rights and well-being of our human subjects

The rights and well-being of our human subjects are protected. They are informed of their rights and how their data is stored. They participate in the study voluntarily. (See Appendix 2 - Participant information and consent form). We exclude vulnerable people whose ability to participate in the study (as detailed in [3.6.3](#)).

The software is noninvasive, built to minimise possible risks to the subject, and akin to many freely available commercial video games for entertainment (see [3.14](#) and Appendix 11 - Ethics evaluation of the study). The subjects have contact channels with the clinical subject coordinators (CSC) and the coordinating investigator.

3.6.6.2 The reported trial data are accurate, complete, and verifiable from source documents

The study is conducted primarily online so that the subjects play the game and complete online questionnaires along predefined instructions, progression, and scheduling dictated by backend server software. Thus, a vast majority of actions and data acquisition during this trial take place automatically and in a manner that is fully traceable in terms of data sources and

time stamping. This alleviates the monitoring burden that is significant for the present trial that is carried out as academic, non-commercial research.

The trial data is gathered online using digital tools that have been developed through Good Programming Practises (GPP) and tested to verify that they produce accurate and complete data. As the subjects enter their information, the information is stored to servers in secure data centres, and their answers can be verified through a database query by an authenticated user inside a dedicated shield server.

The game infrastructure has two server entities:

1. Registration server
2. Game server

Registration server is responsible for the subject registration pipeline, questionnaires and following subjects game time limits. This server is being backed up according to best practises. Database of the registration server is being copied once a week and saved to an external back-up location to preserve the historical accuracy of the data. This guarantees that the data is intact and unchanged over time.

Each of the subjects is assigned a pseudonymised unique username and password upon registration ensuring that only the specified user participates in the intervention. With this username and password combination we can track and validate each of the subjects from the data. The game server uses only the unique pseudonymised username and password.

Game server is responsible for the adaptation of the game. Subjects log in with their unique account credentials and the game client sends and receives data from the game server. Data sent to the game server from the client is time stamped and tracked per user credentials. Data on the game server is being also backed up according to best practises and saved to an external location.

3.6.6.3 Trial compliance

The trial will be conducted in compliance with the currently approved protocol and the present amendment, as well as possible upcoming amendments. This compliance will be ensured by

1) **Training** of the investigators, CSCs, data analysts, and software developers to operate in the context of GCP-compliant RCT research. All staff participating in the conductance of the research are trained to be intimately aware of the CIP and design, and thus the appropriate investigational methods and practises, described in detail in CIP.

2) **Documentation** of, especially, subject- and data-related actions before, during, and after trial. In particular, the actions carried out in patient interactions and investigation monitoring will be documented and deviations from the CIP identified and acted on as described in section 3.10. Similarly, the data processing actions associated with interim and final analyses, and the actions triggered by these events (possible changes to trial structure and reporting demands, respectively) will be carried out in a CIP- and GCP-compliant manner.

3) **Effective communication.** The research team has internal communication channels to facilitate daily, low-threshold communication within the team. The researchers hold recurrent team meetings weekly where the compliance with the CIP is actively reflected.

The trial compliance from the perspective of CIP, GCP, and associated regulations is monitored actively during the study. All research and clinical staff are encouraged to engage in good-faith reporting in case of detection of deviations from CIP or GCP to the coordinating investigator. If a staff violation is detected, the coordinating investigator will follow it up, creating a written report on the incident. Necessary disciplinary actions are taken, the incidence is reflected internally, and research processes are improved to avoid such deviation in the future. A full evaluation of the CIP compliance, cross-referencing the items in this CIP, is conducted annually completed with a written report.

3.7 Statistical considerations

3.7.1 Data descriptors and frequency

Data for the analysis of the clinical study will be collected in the forms of:

1. **Sign-up process.** The online sign-up process is done once at the beginning of the study where the subject gains information regarding the study, signs an informed consent form, and background information is gathered.
2. **Clinical questionnaires.** The subjects fill questionnaires prior to the intervention (T0), and 4 (T1), 8 (T2), 12 (T3), and 24 (T4) weeks from the beginning of the research.
3. **In-game questionnaire.** An in-game questionnaire is presented to the subject after each game level, up to a total of 27 times, please see Appendix 7 - Tutkimuksessa kerättävät tiedot
4. **In-game behaviour.** Behavioural performance scores that are acquired from each completed game.
5. **Clinical interview.** The subjects are interviewed for the inclusion and exclusion criteria before the intervention begins.
6. **Experiential interview.** The subject may opt in to an interview conducted online.

3.7.1.1 Sign-up process

The sign-up is done completely online.

When the subject enters the online study recruitment site, they are first guided to read the recruitment information (Appendix 1 - Recruitment notice). Then, they are guided to read the information regarding the study (Appendix 2 - Participant information and consent form) and asked to read the user agreement (Appendix 3 - Confidentiality obligation and right of use). Should they agree and be willing to participate in the study, they are guided to sign an informed consent form (Appendix 2 - Participant information and consent form).

Then, the subject is asked for their contact information, demographics, mental health history, digital game playing history, and they are asked for their interest to participate in the interview and brain imaging sub-study.

The sign-up process is presented visually in the table 4 below, and the questions are in detail in Appendix 7 - Data collected in the study.

Table 4: Sign-up process (filled once)

	Pre-game period		Playing intervention			Follow-up
Content	Sign up and background questionnaires	T0 Before playing	T1: T0 + 4 weeks	T2: T0 + 8 weeks	T3: T0 + 12 weeks	T4: T0 + 24 weeks
Welcome to to the depression study recruitment page. ("Appendix 1 - Recruitment notice")	x					
Participant information ("Appendix 2 - Participant information and consent form")	x					
Confidentiality obligation and right of use ("Appendix 3 - Confidentiality obligation and right of use")	x					
Study consent form ("Appendix 2 - Participant information and consent form")	x					
Background 1: Contact information and background	x					
Background 2: Mental health	x					
Background 3: Gaming history	x					
Background 4: Brain imaging and interview	x					
Summary of background information	x					

3.7.1.2 Clinical questionnaires

The subjects fill questionnaires prior to the intervention (T0), and 4 (T1), 8 (T2), 12 (T3), and 24 (T4) weeks from the beginning of the research. All questionnaires are answered online.

The subject must fill the questionnaires at T0 before they are randomised into one of the three research arms: the intervention doesn't begin before the subject has filled the questionnaires. At T1, T2, T3 and T4, the subjects have two weeks to fill the questionnaire from the beginning of the time point. If the subject doesn't fill the questionnaire within one week, they are followed up with a phone call.

ASSIST-LITE, PCL-5, and BEAQ are filled only once at T0. The state of care questionnaire is filled in T1, T2, T3, and T4. IEQ measures game experience and is filled only after the subject has played the game. Other clinical questionnaires are filled at T0, T1, T2, T3, and T4. (see also Table 5).

The questionnaires include:

- Immersive experiences questionnaire (IEQ)
- Questionnaire regarding their state of care
- Patient health questionnaire (PHQ-9)
- Quick inventory of depressive symptomatology (QIDS-SR16)
- General anxiety disorder questionnaire (GAD-7)
- Positive valence systems scale (PVSS)
- The ruminative response scale (RRS)
- Alcohol, smoking and substance involvement screening test lite (ASSIST-LITE)
- PTSD checklist for DSM-5 (PCL-5)
- Brief experiential avoidance questionnaire (BEAQ)
- Sheehan disability scale (SDS)
- Well-being index (WHO-5)
- 7 item game addiction scale (GAS)

For details when the subjects are asked to fill the questionnaire, see table 5. For the questionnaire descriptions see 3.6.5.1, and for questionnaire content, see Appendix 7 - Data collected in the study.

Table 5: Clinical questionnaires

	Content	Sign up and background questionnaires	T0 Before playing	T1: T0 + 4 weeks	T2: T0 + 8 weeks	T3: T0 + 12 weeks	T4: T0 + 24 weeks
1	Immersive experiences questionnaire (IEQ)			MEL-T01 MEL-S01	MEL-T01 MEL-S01	MEL-T01 MEL-S01	TAU
2	Treatment status -questionnaire			x	x	x	x
3	Patient health questionnaire (PHQ-9)		x	x	x	x	x
4	Quick inventory of depressive symptomatology (self-report) (QIDS-SR16)		x	x	x	x	x
5	General anxiety disorder questionnaire (GAD-7)		x	x	x	x	x
6	Positive Valence Systems Scale (PVSS)		x	x	x	x	x
7	Short-version ruminative response scale (RRS)		x	x	x	x	x
8	Alcohol, Smoking and Substance Involvement Screening Test (ASSIST-LITE)		x				
9	PTSD Checklist for DSM-5 (PCL-5)		x				
10	Brief experiential avoidance questionnaire (BEAQ)		x				
11	Sheehan disability scale (SDS)		x	x	x	x	x
12	The world health organisation -five well-being index (WHO-5)		x	x	x	x	x

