3.10.1 Subjects deviations or violations

The majority of human made deviations are mitigated because the majority of the intervention is digital: answering questionnaires as well as playing the game. Wherever possible, we have mitigated the possibility for the subject to deviate from the CIP.

Before the subject is included in the research, they complete the signup process (see 3.7.1.1), first set of clinical questionnaires (see 3.7.1.2), and their MDD diagnosis is confirmed through clinical interview (see 3.7.1.5). Only then the subject is randomised to MEL-T01, MEL-S01, or TAU group, and they are given access to the intervention (for groups MEL-T01 and MEL-S01). Thus we mitigate the risk of the subject not meeting the inclusion/exclusion criteria.

When the subject arrives at T1, T2, T3, and T4, they are emailed the instructions to complete clinical questionnaires. In addition, the reminder to complete the questionnaires is shown to the MEL-T01 and MEL-S01 group in the game, and they are not able to make progress until they have completed the questionnaires. The questionnaires are filled online. If the subject doesn't fill the questionnaires in 7 days from the onset of T1, T2, T3, or T4, they are followed up with a phone call by the CSC.

The subject is recommended to play the game for 48 hours during the 12 week play period. To be included in the sample we require 24 hours of gameplay. When the subject is contacted by the CSC, the CSC has access to the subject total game time and number of weeks played (but they do not know the subject group). If the subject total game time divided by the number of weeks played is less than 2 (the minimum required), the CSC kindly discusses the topic with the subject encouraging them towards reaching 24-48 hours of playing time during the 12 week play period.

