3.11 Accountability

3.11.1 Control of access to the device

Access to the software is only available as long as the digital key is valid. The digital key can be activated and deactivated remotely by the researchers. Only one install is possible with one digital key. Deactivated key prevents launching the software. The researchers can deactivate the subject's key if the subject doesn't follow the researchers instructions. Access to the game requires login to the distribution channel (Steam) and login to the game client itself.

Access to the MEL-T01 and MEL-S01 software is restricted to subjects who have completed the signup pipeline, T0 questionnaires, and gone through the clinical interview by the CSC. After this, the subjects are randomised to one of the three groups.

Whether in TAU, MEL-T01, MEL-S01 group, the access to the training is 12 weeks from the beginning of the intervention. For 2 weeks after the intervention has ended, the access to the training is denied from the user, but they can access the main menu through which they can complete the questionnaire T3 (groups MEL-T01 and MEL-S01) or T4 questionnaire (TAU group).

After the two weeks are over, the access to the software is denied, and the subject can uninstall it from their device. See Table 6 for a detailed outline of the access to the device.

Table 6: Access to the device

Access to the device											
Study arms	T0 (Before playing)	T1: T0 + 4 weeks	T2: T0 + 8 weeks	T3: T0 + 12 weeks	T3 + 2 weeks	T4: T0 + 24 weeks	T4 + 2 weeks.	After T4 + 2 weeks			
MEL-T01 intervention	T0 begins after CSC confirms the subject is eligible to the study. The subject is randomised to one of the three groups.	MEL-T01 intervention				Access to menu only.	No access to the device.				
MEL-S01 intervention		MEL-S01 intervention				Access to menu only.	No access to the device.				
Treatment as usual ("TAU")		Treatment as usual				Access to MEL-T01 or MEL-S01 intervention		Access to menu only.	No access to device.		

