3.14 Safety reporting

3.14.1 Safety reporting procedures and timelines

For AE and SAE definitions, see 3.3.

The subjects are given health information regarding the device in the game (see Appendix 6 - Investigator's brochure). Should the subject experience an anticipated or unanticipated AE or an SAE, or an assumed or observed device deficiency, they are able to report them through the channels below. The subjects can:

- Provide any free-form feedback in in-game questionnaires presented 28 times during the intervention, which are monitored by the CSCs.
- Report game-related issues digitally into a Jira-based system that is accessible through the in-game main menu which is monitored by the CSCs.
- Describe their concerns in both subject-initiated and pre-scheduled (weeks 0, 4, 8, 12, and 24) phone calls with the CSCs.
- Send email to CSCs by using an email address presented both in the game main menu and in the subject's informed consent form.

The CSCs actively monitor these channels on a daily basis from Monday to Friday between 9-17 o'clock. When the subject indicates an AE, SEA, or device deficiency, the event is recorded into a secure, traceable digital system.

Timelines. The summary report for AE is delivered to the coordinating investigator on a weekly basis for review. AE that merit investigations are reported immediately to the coordinating investigator. All SAE are reported immediately to the coordinating investigator both verbally as well as in written reports.

Records. Coordinating investigators keeps a full digital record of any AE, SAE, and device deficiency. The coordinating investigator is responsible for evaluating whether the AE or SAE has a causal connection with the device use. The causality is evaluated on a scale of **possible**, **probable**, and **definitive**. In addition, the AE is evaluated for its severity from **mild** effects that are easily tolerated, **moderate** where there is discomfort, and **severe** that has significant effects. All device deficiencies are evaluated for the possibility of AE and SAE.

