3.15 Criteria and procedures for follow-up

3.15.1 Subjects following the end

The MEL-T01 and MEL-S01 have a 12 week follow-up period after the playing intervention between T3 and T4. TAU has a playing period between T3 and T4.

All subjects are emailed after they have filled the T4 questionnaire when the study period ends for all of the groups. In this email, the subjects are told about the randomisation as well as which group they belonged to as explained in Appendix 2 (Participant information and consent form). The subject is informed that the research results will be published later. The

subject is asked for feedback regarding the study, and their questions regarding the study are answered. The subject is thanked for their participation. The subject is asked for feedback regarding the study, and their questions regarding the study are answered via email or phone.

The subject is compensated for their participation based on Social and health ministry 82/2011 §2: 50€ if they have played the game for at least 24 hours and answered all questionnaires; or 120€ if they have played the game at least 48 hours and answered all questionnaires.

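### TAU subjects play the device in weeks 12–24 with no questionnaire-driven suicidality check inside play, and their T3 PHQ-9 can be answered after play has begun

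*Combined protocol and SAP*

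**What the plan says.** **Schedule.** Section 3.7.1.2 places the repeated questionnaires at T0 and then "4 (T1), 8 (T2), 12 (T3), and 24 (T4) weeks from the beginning of the research", with no separate schedule for TAU on the PHQ-9 or the other repeated scales. Each time point has a window: "At T1, T2, T3 and T4, the subjects have two weeks to fill the questionnaire from the beginning of the time point".

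**TAU device period.** Section 3.15.1 states that "TAU has a playing period between T3 and T4". The synopsis, Table 1 and Table 6 agree: TAU subjects receive MEL-T01 or MEL-S01 for 12 weeks from T3.

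**End of access.** Under 3.11.1, "For 2 weeks after the intervention has ended, the access to the training is denied from the user". The main menu stays open so that game-arm subjects can complete T3, and TAU subjects T4, with training closed.

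**Alert.** Section 3.6.3.5 monitors answers to the clinical questionnaires. An answer showing suicidal ideation leads to support text and contact by the clinical subject coordinator (CSC). Section 3.6.4.3 gives the CSC access to those responses. Section 3.6.3.4 lists suicidality among the grounds for discontinuing a subject.

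**Calls.** Section 3.14.1 lets subjects "Describe their concerns in both subject-initiated and pre-scheduled (weeks 0, 4, 8, 12, and 24) phone calls with the CSCs". Section 3.7.1.2 instead describes a call that is conditional on unfilled forms: if they are not completed "within one week, they are followed up with a phone call".

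**Lock.** Under 3.10.1 the questionnaire reminder is "shown to the MEL-T01 and MEL-S01 group in the game, and they are not able to make progress until they have completed the questionnaires".

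**The concern.** The schedule is counted from T0, but device exposure is not. In the game arms the alert can prompt a decision to stop at about weeks 4 and 8 of play. A TAU subject who worsens during play and does not say so reaches the alert only at T4, when access has ended or is ending. This bears on the plan's own rules, because 3.6.5.2 admits subjects with suicidal thoughts whom the CSC judges not to intend acting on them.

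A second matter comes from the same calendar. T3 is the TAU arm's primary time point and the start of the exploratory T3–T4 change (3.5). Access opens at T3, the T3 forms stay open for two more weeks, and no text makes access wait for them. A T3 answer given after play has begun is not a clean pre-device value. If the device relieves symptoms, such answers would pull the TAU value towards the game arms.

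**Working it through.** The plan states no figure for this, so the check is a count on its calendar.

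**Inputs**
- Questionnaires at weeks 0, 4, 8, 12 and 24; answer windows T1 4–6, T2 8–10, T3 12–14, T4 24–26 (3.7.1.2).
- Device access: game arms weeks 0–12, TAU weeks 12–24 (3.11.1, Table 6).
- Recommended dose 4 h per week; daily maximum 1.5 h (synopsis).
- 800 subjects in blocks of six, two per arm (3.6.4.2); assumed dropout 50% (3.7.4.1).

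**Time points strictly inside play**
- Game arms: weeks 4 and 8, so 2.
- TAU: none of 0, 4, 8, 12 and 24 lies between 12 and 24, so 0. The call weeks in 3.14.1 are the same, so they also give 0. If the conditional call in 3.7.1.2 and 3.10.1 governs, no form falls due between the T3 window and T4 to trigger one.

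**Longest stretch of play without an answer, forms returned within their windows**
- Game arms: the largest of t1, t2 − t1 and 12 − t2, with t1 in 4–6 and t2 in 8–10. The minimum is 4 weeks (t1 = 4, t2 = 8) and the maximum 6 weeks (for example t1 = 6, t2 = 10).
- TAU: 24 − 12 = 12 weeks if T3 is answered at week 12; 24 − 14 = 10 weeks if at week 14.
- At 4 h per week: game arms 16 to 24 h; TAU 40 to 48 h.

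These stretches run from the opening of access, so they do not depend on how long before access the T0 forms were filled, a lag the plan does not state.

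**Interval between T3 and T4 answers**
- 24 − 14 = 10 to 26 − 12 = 14 weeks, identical in all three arms. Only TAU subjects have the device during it.

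**Play possible before a late TAU T3 answer**
- Up to 14 days: 2 × 4 = 8 h at the recommended dose, 14 × 1.5 = 21 h at the daily maximum. The latter needs maximal play every day.

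**Number of TAU device users**
- 800 × 2/6 = 267 with full retention to T3, or 267/800 = 33% of device users.
- If 25% of TAU dropped out before T3 (assumption): 200/733 = 27%. If 50% (assumption): 133/667 = 20%.
- These count people on this schedule, not people harmed.

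**The case against.** **All arms have the same assessments and the same late gap.** This stands. Each arm gets five assessments, TAU subjects have four of them by device start, and the T3–T4 interval is as long in the game arms. A reader might infer that TAU is assessed less often or has uniquely wide spacing; neither is so. The asymmetry lies only in where the assessments fall relative to device use.

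**The gap matters only if play adds risk, and none is shown.** This largely stands. Suicidality is not among the anticipated adverse events (3.3.1.2), the 54-patient feasibility study reported no serious events (3.3.1.1), and device risk is rated low (3.3.1.6). The documents do not support a claim that the device provokes suicidality. What remains is that the plan makes suicidality a ground for stopping and checks for it during play in two arms but not the third.

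**TAU subjects are not unmonitored.** Also correct. Threat of self-harm is excluded at interview, a treatment contact is mandatory (3.6.3.1), and CSCs read in-game free text, issue reports and email on weekdays (3.14.1). But the trial's own channels depend on the subject raising the matter. The in-game form asks about enjoyment and difficulty (3.7.1.3), and none of these channels is described as a suicidality screen.

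**The T3 point rests on silence.** Section 3.6.6.2 says backend software dictates progression and scheduling, so a gate may exist in the software. The text does not say so. A reader might infer that TAU T3 values are in fact contaminated, or that the lock does not cover TAU subjects. The documents show only that the written rules permit the first and leave the second open. The share of late T3 answers is not given.

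**Conclusion.** The point holds as a modest gap in scheduled monitoring plus a separate opening for late TAU T3 answers. The alert has 0 time points inside TAU play against 2 in the game arms, with 10–12 against 4–6 weeks of play without an answer. A TAU T3 PHQ-9 can follow up to 14 days of device use. The counts assume forms returned within their windows and access as in Table 6. The number affected is at most 267, and 133 if the plan's 50% dropout applied to TAU before T3.

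Confidence is medium. Appendices 5, 7 and 11 could not be checked. The current version (February 2024) also postdates the planned completion of 31.12.2023, so how many TAU subjects had yet to play is unknown.

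**What to change.** 1. **3.11.1 and Table 6.** Open TAU device access when the T3 questionnaires are completed, or at the close of the two-week T3 window if they are not, so that non-responders still reach the device. Keep 12 weeks of access from opening. State whether TAU T4 stays at week 24 or moves with access, since a late starter's access would run to as late as week 14 + 12 = 26.
2. **3.7.1.2 and Table 5.** Issue the existing online PHQ-9, with the existing CSC alert, to TAU subjects 4 and 8 weeks after access opens (about weeks 16 and 20), for safety monitoring only. State that these forms do not count towards the payment rule in 3.15.1, which requires every questionnaire to be answered.
3. **3.10.1.** State that the in-game completion lock also applies to TAU subjects while they play.

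**Benefit.** For subjects starting at week 12, time points inside TAU play rise from 0 to 2 and the nominal gap falls from 12 to 4 weeks, as in the game arms.

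**Cost.** Two nine-item forms per TAU device starter (2 × 133 = 266 to 2 × 267 = 534 in total), the CSC follow-up they trigger, backend rescheduling and an amendment. Late T3 responders start up to two weeks later. Assessment frequency becomes unequal between arms in the exploratory T3–T4 period. An alert at week 16 or 20 may let a CSC infer TAU status, to which 3.6.4.3 blinds them, though not which device is in use; 3.6.4.1 says investigators already know who is in TAU. The T0–T3 primary endpoint definition is unchanged and no new instrument is needed.
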